9.2.2 Neutralizing anti-bimekizumab antibodies

NAb will be assessed using IL-17AA- and IL-17FF-specific assay methods, respectively. NAb results will be positive or negative to each specific NAb assay or both.

Any NAb results derived from samples with drug concentrations > the drug tolerance limits of the NAb assays (100 μ g/mL) will be labeled 'inconclusive'. All inconclusive results will be regarded as missing.

Subjects will be assigned an overall Neutralizing anti-BKZ antibodies (NAb) classification, inclusive of Baseline and post-Baseline results from NAb assay:

- NAb negative: No NAb positive samples for IL-17AA and IL-17FF at Baseline or post-Baseline. This group will also include subjects who have only 1 missing sample and all other available samples during the period of interest are negative. Study participants who are NAb negative will be classified as follows:
 - ADA_b positive / NAb negative: ADA_b positive subjects who are 1) NAb negative for all available ADA_b positive samples or 2) with only one missing NAb sample and all other evaluated ADA_b positive samples are NAb negative.
 - ADA_b negative: if the subject has all the samples as ADA_b negative or only one missing/inconclusive sample with all other available samples as negative ADA_b. Note that ADA_b negative samples are not subject to the neutralizing assay.
- NAb positive: One or more positive samples (IL-17AA positive, IL-17FF positive, or both) at Baseline or post-Baseline (regardless of missing samples). Study participants who are NAb positive will be further classified as follows:
 - Positive for IL-17AA only: one or more positive samples for IL-17AA at baseline or post-baseline. No positive samples for IL-17FF
 - Positive for IL-17FF only: one or more positive samples for IL-17 FF at baseline or post-baseline. No positive samples for IL-17AA
 - Positive for both IL-17AA and IL-17FF: one or more positive samples for both IL-17AA and IL-17FF at baseline or post-baseline
- NAb Missing:

- >1 relevant NAb samples are missing/inconclusive and other available NAb samples during the period of interest are negative, eg, missing or insufficient sample left for NAb testing.

Note: For PK and efficacy analyses up to a certain timepoint (Week 16, 24 and 52) by NAb status, only data up to the timepoint of interest will be utilized in deriving the subject's overall NAb status during that period (eg for the ACR50 by NAb up to Week 16, only NAb data from baseline up to Week 16 will be used to derive subject's overall NAb status during the DBP).

- A listing will be produced to summarize the NAb status overall in the study. The listing will be sorted by treatment group (Placebo/ BKZ 160mg Q4W vs. BKZ 160mg Q4W), subject identifier and visit and will summarize the following information for each subject assessed for NAb:
 - Visit
 - Study week
 - Laboratory sampling date and time
 - Time since previous dose (weeks)
 - The corresponding BKZ plasma concentration level at each visit (ug/mL)
 - Anti-BKZ anti-body titer at each visit
 - IL-17AA NAb status and corresponding IL-17AA signal/negative control result
 - IL-17FF NAb status and corresponding IL-17FF signal/negative control result
- A summary table will provide the following overall summary statistics by treatment group (Placebo/ BKZ 160mg Q4W vs. BKZ 160mg Q4W) (based on the total number of randomized subjects):
 - The number and percentage of subjects confirmed as anti-BKZ antibody positive and anti-BKZ antibody negative up to Week 16, 24, 52 (excluding SFU), 52 (including SFU)
 - The number and percentage of subjects who are NAb positive, NAb negative and missing up to Week 16, 24, 52 (excluding SFU) and 52 (including SFU).

The NAb summary tables will be repeated with percentages calculated on a denominator based on the number of ADAb positive subjects during the above periods.

In addition, the following analyses will be performed to assess the impact of NAb status on efficacy variables:

- Two figures (side by side) summarizing efficacy response (ACR50 based on NRI) versus time for each treatment group (Placebo / BKZ 160mg Q4W and BKZ 160mg Q4W) by NAb status (ADA_b negative, NAb positive, ADA_b positive / NAb negative, missing) will be created. If $\geq 95\%$ of subjects are included in the non-missing groups, the missing group will not be displayed in the figure. Separate figures will be presented for data up to Week 16 (for the BKZ 160mg Q4W group), and to Week 24 and 52 by treatment group (BKZ 160mg Q4W vs. Placebo / BKZ 160mg Q4W). The analyses will be repeated for ACR20 and PASI90 (for

PASI90, in the subgroup of subjects with PSO involving at least 3% BSA at Baseline). The data will be also presented in a tabular format.

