- A summary table displaying the number and percentage of subjects with ADA_b status - positive, negative, total of positive and negative , missing - at each visit (including SFU) and overall will be provided. For the overall summary at any visit, 2 summaries will be presented:

- Including any visit during the treatment period (as defined in [Section 3.1](#)). Thus, this summary will exclude data obtained at the SFU visit and will include data obtained at Baseline. This summary will display the overall ADAb status up to Week 16 (for the BKZ 160 mg Q4W group), and to Week 24 and 52 by treatment group (BKZ 160 mg Q4W, Placebo / BKZ 160 mg Q4W).
- Including any visit during the study. Thus, this summary will include data obtained at both the SFU visit and at Baseline. Subjects who rolled over to the OLE study will not have a SFU visit per study protocol. For these subjects, the ‘overall ADAb status including SFU’ will then be considered as being identical to the ‘overall ADAb status up to Week 52’.

For the overall ADAb status, a subject will be classified as:

- Positive if the subject has at least one positive sample at any time in the treatment period (regardless of having missing /inconclusive data)
- Negative if the subject has all the samples negative or only one missing/inconclusive sample with negative ADAb samples up to the timepoint of interest
- Missing if the subject has missed more than one sample result for ADAb assessment (or have more than one inconclusive sample) and all other available ADAb samples are negative during the period of interest (If there are $\geq 95\%$ of subjects included in the non-missing groups, the missing group will not be displayed on the table).

- The above summary table displaying the number and percentage of subjects in each of the ADAb status (positive, negative, total of positive and negative, missing) will be repeated for the subjects randomized in Japan for Placebo / BKZ 160 mg Q4W and BKZ 160 mg Q4W groups (overall summaries only). The overall summary excluding SFU will be generated for up to Week 16, 24 and 52.
- A summary table displaying the number and percentage of subjects in each of the ADAb status (positive, negative, total of positive and negative, missing) by concomitant medications (use of cDMARDs at entry, use of MTX at entry, use of oral/systemic corticosteroids at entry) will be provided (overall summaries only, including summaries up to Week 16, 24, 52 and SFU).

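### SAP Section 9.2.2 lets an ADAb-positive subject with one antibody-positive sample and no valid NAb result count as NAb negative (or go unclassed) instead of NAb Missing

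*SAP*

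**What the plan says.** Section 9.2.2 defines the top-level class by the absence of a positive: "NAb negative: No NAb positive samples for IL-17AA and IL-17FF at Baseline or post-Baseline". It then tolerates a gap: "This group will also include subjects who have only 1 missing sample and all other available samples during the period of interest are negative". For ADAb-positive subjects the second limb of the sub-class repeats the tolerance: "with only one missing NAb sample and all other evaluated ADA_b positive samples are NAb negative".

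The missing class has a higher threshold: ">1 relevant NAb samples are missing/inconclusive and other available NAb samples during the period of interest are negative".

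Three further rules decide which samples count:
- ADAb-negative "samples are not subject to the neutralizing assay" (Section 9.2.2).
- NAb results at drug concentrations above 100 µg/mL are inconclusive, and "All inconclusive results will be regarded as missing" (Section 9.2.2).
- One positive sample makes a subject ADAb positive: "Positive if the subject has at least one positive sample at any time in the treatment period" (Section 9.2.1, overall ADAb status).

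The worked example in Section 9.1 follows the same default. A subject without a positive IL-17AA or IL-17FF sample is given NAb-negative status for the period.

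**The concern.** Allowing one missing sample is harmless when other samples carry the evidence. For NAb, the relevant samples are only the ADAb-positive ones, and a subject may have just one. If that one has no valid result, the tolerance uses up all the evidence and the subject is called negative with nothing behind the label.

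NAb status splits the BKZ concentration tables and figures (Section 9.1), the ACR50, ACR20 and PASI90 displays (Section 9.2.2) and the TEAE table by NAb status (Section 10.2.1). Each would hold subjects of unknown status in its NAb-negative group.

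**Working it through.** **1. Applying the rules literally.** For an ADAb-positive subject, let k be the number of ADAb-positive samples. Each NAb result is positive, negative, or missing (which includes inconclusive). Any positive gives NAb positive, so only patterns without a positive matter.

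| k | NAb results | Valid results | Class under Section 9.2.2 |
|---|---|---|---|
| 1 | negative | 1 | NAb negative |
| 1 | missing | 0 | NAb negative (second limb met because there is no other sample) |
| 2 | negative, negative | 2 | NAb negative |
| 2 | negative, missing | 1 | NAb negative |
| 2 | missing, missing | 0 | NAb Missing |
| 3 | negative, negative, negative | 3 | NAb negative |
| 3 | negative, negative, missing | 2 | NAb negative |
| 3 | negative, missing, missing | 1 | NAb Missing |
| 3 | missing, missing, missing | 0 | NAb Missing |

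In the second row the subject cannot be NAb Missing, because 1 is not more than 1, and cannot be NAb positive. The top-level definition and the Section 9.1 example both give NAb negative. The result is out of order: no valid result out of one is negative, while one valid negative out of three is Missing.

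**2. Effect on the percentages.** Section 9.2.2 bases the summary on all randomized subjects and repeats it on all ADAb-positive subjects. Call the denominator N, the positive count P, the negative count X, the missing count Y, and the misplaced subjects m. Reclassifying them gives P/N (unchanged), (X − m)/N and (Y + m)/N. Only the negative and missing rows move.

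**3. How such a case arises.** A missed visit cannot produce it, because the sample must already have been collected and confirmed ADAb positive. Two routes remain.
- *Inconclusive result.* Section 10.1.1.2 equates 140 days with five half-lives, so the half-life is 140/5 = 28 days, equal to the Q4W interval. The amount in the body at trough is then at most 160 × (1/2 + 1/4 + …), which stays below 160 mg even with full absorption. A trough above 100 µg/mL (100 mg/L) would need a distribution volume under 160/100 = 1.6 L, which I take to be implausible in an adult. The scheduled on-treatment ADAb weeks in Section 2.2.4 (4, 8, 12, 16, 20, 24, 36, 52) fall at trough. This route is nearly empty.
- *Insufficient sample or assay failure.* This is the main remaining source.

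**4. Illustrative size.** The SAP gives no inputs, so these are assumptions. Take 100 ADAb-positive subjects without a NAb-positive result. Suppose 10–50% have a single ADAb-positive sample and 2–10% of those lack a valid NAb result.
- Low: 100 × 0.10 × 0.02 = 0.2 subjects.
- High: 100 × 0.50 × 0.10 = 5 subjects.

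Shorter windows probably contain more single-positive subjects. The schedule gives five ADAb samples from Baseline to Week 16. It gives only three (Weeks 16, 20, 24) for the Placebo / BKZ group up to Week 24.

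**The case against.** *The second limb presupposes another evaluated sample.* That is a natural reading. The subject then falls outside that limb, but is still not NAb Missing. The top-level definition still returns NAb negative; if that is set aside too, the subject has no class. The text needs repair either way.

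*Tolerating one missing sample is a deliberate convention.* It is: the ADAb rules in Sections 9.1 and 9.2.1 use it too. There, every scheduled sample counts, so one gap normally leaves others. For NAb the count can be one.

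*Section 9.2.1 treats a subject with a single positive sample as ADAb negative.* That definition serves the efficacy-by-ADAb displays. Section 9.2.2 has its own ADAb-negative definition, which a subject with a positive sample does not meet.

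*The case is rare, visible and descriptive.* This stands. Section 9.2.2 requires a listing of IL-17AA and IL-17FF status by visit, and none of these outputs is in the hierarchy of Section 4.5.

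**Conclusion.** The rule gives a wrong label, or none, to one identifiable pattern: a single ADAb-positive sample without a valid NAb result. It overstates the NAb-negative count, understates the missing count and mixes unknown status into the NAb-negative group of descriptive outputs. This is a minor point. The number affected is not given and is probably small; the 0.2 to 5 per 100 rests wholly on assumed rates.

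A reader might infer three stronger things that the SAP does not support:
- *That reported NAb incidence is lowered.* The fixed denominators leave the NAb-positive percentage unchanged.
- *That the NAb-negative group is pulled towards the NAb-positive one.* This would require some of these subjects to be truly NAb positive, and nothing in the SAP shows it.
- *That these subjects were never tested.* An inconclusive sample was assayed; the accurate description is that there is no valid result.

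**What to change.** Add one sentence to Section 9.2.2: the class 'ADAb positive / NAb negative' requires at least one valid negative NAb result, and an ADAb-positive subject with no valid NAb result is 'NAb Missing' whatever the number of missing samples. Align the NAb-negative example in Section 9.1.

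Among the patterns tabulated, only the single-sample missing case changes class. The cost is a slightly larger missing group. The efficacy figures drop that group when at least 95% of subjects are non-missing, and the TEAE table by NAb status names no missing category. A footnote with the number of NAb Missing subjects would keep them visible in both.

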10 SAFETY ANALYSES

All safety summaries will be done on all subjects in the SS.

10.1 Extent of exposure

The extent of exposure will be evaluated based on the duration of exposure to study drug and the time at risk.

Summaries for exposure will be presented:

- For the DBP on the SS by treatment group,
- For the ATP on the ATS by treatment group and for all BKZ treated subjects
- For the AMP on the AMS by treatment group and for all BKZ treated subjects.

The following results will be presented:

- A descriptive summary of duration of study treatment exposure in days,
- A total study medication duration in subject-years,
- The number of subjects exposed to the following duration of study treatment (for the DBP and ATP together):
 - > 0 week
 - ≥ 16 weeks
 - ≥ 24 weeks
 - ≥ 36 weeks
 - ≥ 48 weeks
 - ≥ 52 weeks
- A descriptive summary of time at risk in days,
- A total time at risk in subject-years.

A by-subject listing of date of first and last dose, the duration of exposure and the time at risk will be performed.

Throughout the below sections, date of last clinical contact for each subject is defined as the maximum of the following dates:

- Date of last visit including SFU visit,
- Last imputed AE start date,
- Date of study termination/completion,
- Last date of study drug administration.

- Or any other collected date.

In calculation of exposure detailed below, 14 days refers to the time between 2 consecutive study treatment administrations.

10.1.1 Double-Blind Treatment Period

10.1.1.1 Study medication duration (days)

The study medication duration will be calculated as:

- For subjects with a date of last dose in the DBP +14 days beyond the date of first dose in the ATP (excluding SFU):

$$\text{Date of first dose (ATP)} - \text{Date of first dose (DBP)} + 1$$

- For subjects with a date of last dose in the DBP +14 days before or on the same day as the date of first dose in the ATP (excluding SFU):

$$\text{Date of last dose (DBP)} - \text{Date of first dose (DBP)} + 14$$

- For subjects who have died during the DBP:

$$\text{Date of death} - \text{Date of first dose (DBP)} + 1$$

- For other subjects:

$$\text{Date of last dose (DBP)} - \text{Date of first dose (DBP)} + 14$$

- For other subjects who withdrew from study or ongoing in the study during DBP, the minimum between:

$$\text{Date of last dose (DBP)} - \text{Date of first dose (DBP)} + 14$$

$$\text{Date of the final visit (excluding SFU)} - \text{Date of first dose (DBP)} + 1$$

10.1.1.2 Time at risk (days)

The time at risk will be calculated as:

- For subjects who completed the DBP and continue in the ATP:

$$\text{Date of first dose (ATP)} - \text{Date of first dose (DBP)} + 1$$

- For subjects who have died prior to the final visit of the DBP:

$$\text{Date of death} - \text{Date of first dose (DBP Period)} + 1$$

- For all other subjects (who discontinue on or prior to the final visit of the DBP), the minimum between:

$$\text{Date of last clinical contact} - \text{Date of first dose (DBP)} + 1$$

$$\text{Date of last dose (DBP)} - \text{Date of first dose (DBP)} + 141$$

$$\text{Total number of days in the DBP (112 days)}$$

Note: 140 days refer to 5 times the half-life of BKZ.

10.1.2 Active Treatment-blind Period

The exposure will be calculated for subjects in the ATS only.

10.1.2.1 Study medication duration (days)

The study medication duration will be calculated as:

- For subjects who completed the study, with a date of last dose +14 days beyond the date of final visit of the ATP (excluding SFU):

Date of final visit (ATP) – Date of first dose (ATP) + 1

- For subjects who have died during the ATP:

Date of death – Date of first dose (ATP) + 1

For other subjects *Date of last dose (ATP) – Date of first dose (ATP) + 14*

10.1.2.2 Time at risk (days)

The time at risk will be calculated as:

- For subjects who completed the study (and continue into the OLE study):

Date of final visit (ATP) – Date of first dose (ATP) + 1

- For subjects who have died prior to the final visit of the ATP:

Date of death – Date of first dose (ATP) + 1

- For all other subjects (subjects who discontinue early from the study, subjects who complete study as planned but chose not to continue into the OLE study, or subjects who are ongoing in the SFU period at the time of the data snapshot), the minimum between:

Date of last clinical contact – Date of first dose (ATP) + 1

Date of last dose (ATP) – Date of first dose (ATP) + 141

Note: 140 days refer to 5 times the half-life of BKZ.

10.1.3 Double-blind and the Active Treatment-blind Periods (combined)

10.1.3.1 Study medication duration (days)

The study medication duration (in days) for subjects who do not switch study treatment at Week 16 will be calculated as:

- For subjects who completed the study with a date of last dose +14 days beyond the date of final visit date (excluding SFU):

Date of final visit – Date of first dose + 1

- For subjects who have died:

Date of death – Date of first dose + 1

- For other subjects:

Date of last dose – Date of first dose + 14

The study medication duration (in days) for Placebo subjects who switch study treatment at Week 16 will be calculated as:

For the DBP (attributed to the Placebo treatment):

- For subjects with a date of last dose +14 days beyond the date of final visit date (excluding SFU):

Date of first dose (ATP) – Date of first dose (DBP) + 1

- For other subjects:

Date of last dose (DBP) – Date of first dose (DBP) + 14

For the ATP (attributed to the BKZ treatment):

- Use the algorithm specified for the ATP.

10.1.3.2 Time at risk (days)

The time at risk (days) for subjects who do not switch study treatment at Week 16 will be calculated as:

- For subjects who completed the study (and continue into the OLE study):

Date of final visit – Date of first dose + 1

- For subjects who have died prior to scheduled final visit date of the ATP:

Date of death – Date of first dose + 1

- For all other subjects (subjects who discontinue early from the study, subjects who complete study as planned but chose not to continue into the OLE study, or subjects who are ongoing in the SFU period at the time of the data snapshot), the minimum between:

Date of last clinical contact – Date of first dose + 1

Date of last dose – Date of first dose + 141

The time at risk (days) for Placebo subjects who switch study treatment at Week 16 will be calculated as:

For the DBP (attributed to the Placebo treatment):

- For all subjects:

Date of first dose (ATP) – date of first dose (DBP) + 1

For the ATP (attributed to the BKZ treatment):

- Use the algorithm specified for the ATP.

10.1.4 Exposure and time at risk in subject-years

The sum of all durations of exposure (in subject-years) will be calculated as:

$$\frac{\sum_{Subjects} \text{Duration of exposure (days)}}{365.25}$$

The sum of all times at risk (in subject-years) will be calculated as:

$$\frac{\sum_{Subjects} \text{Times at risk (days)}}{365.25}$$

10.1.5 Time at risk in subject-years by COVID-19 pandemic period

The time at risk will be determined by COVID-19 pandemic period as defined in [Section 3.11](#).

10.1.5.1 Time at Risk in the pre-COVID-19 pandemic period

Only subjects starting study drug during the pre-COVID-19 pandemic period will have a time at risk calculated during that period.

- For subjects with date of last dose of study drug on or after 11mar2020:

$$10\text{mar}2020 - \text{date of first dose} + 1$$

- For subjects who have died on or before 10mar2020:

$$\text{Date of death} - \text{date of first dose} + 1 \text{ (If the date of death is later than 140 days following the last dose of BKZ, this rule does not apply).}$$

- For subjects with date of last dose of study drug on or before 10mar2020 but with the earliest date between (date of last dose + 141) and (date of last clinical contact) on or after 11mar2020:

$$10\text{mar}2020 - \text{date of first dose} + 1$$

- For subjects with date of last dose of study drug on or before 10mar2020 but with the earliest date between (date of last dose + 141) and (date of last clinical contact) on or before 10mar2020, minimum between:

$$\text{date of last dose} + 141 - \text{date of first dose}$$

$$\text{date of last clinical contact} - \text{date of first dose} + 1$$

10.1.5.2 Time at Risk in the COVID-19 pandemic period

Subjects with study drug period overlapping the COVID-19 pandemic periods will have a time at risk calculated during that period.

- For subjects with date of last dose of study drug on or after 11mar2020, minimum between:

$$\text{Minimum}(\text{date of last dose} + 141, \text{COVID-19 pandemic end date}) - \text{maximum of} (11\text{mar}2020, \text{date of first dose})$$

$$\text{Minimum}(\text{date of last clinical contact}, \text{COVID-19 pandemic end date}) - \text{maximum of} (11\text{mar}2020, \text{date of first dose}) + 1$$

- For subjects who have died on or after 11mar2020:

$$\text{Minimum}(\text{Date of death}, \text{COVID-19 pandemic end date}) - \text{maximum of} (11\text{mar}2020, \text{date of first dose}) + 1 \text{ (If the date of death is later than 140 days following the last dose of BKZ, this rule does not apply).}$$

- For subjects with date of last dose of study drug on or before 10mar2020 but with the earliest date between (date of last dose + 141) and (date of last clinical contact) on or after 11mar2020, minimum between:

Minimum(date of last dose+ 141, COVID-19 pandemic end date) - 11mar2020

Minimum(date of last clinical contact, COVID-19 pandemic end date) - 11mar2020+1

